9.12 Safety Oversight

The Medical Monitor will review all adverse events and adverse device events that are reported during the study. SAEs will typically be reviewed within 24-hours of reporting. Upon receipt of the SAE Report Form, the Medical Monitor will determine whether the event is unanticipated based on the investigator brochure (IB).

A listing of all AEs will be reviewed periodically by the Medical Monitor as part of routine safety signal detection.

10 STOPPING CRITERIA

10.1 Participant Discontinuation of Study Participation

In the case of a USADE for Intervention group participants, the Medical Monitor will determine if the use of the investigational device will be suspended while the problem is diagnosed. The use of the investigational device may continue if the Medical Monitor believes the event is explainable, unlikely to reoccur and that it is safe for the participant to continue using the device. Alternatively, the Medical Monitor may request the study participant, or all study participants, to stop using the investigational device or to only use in Manual Mode. Should Intervention group study participants be required to stop using the study device or to only use in Manual Mode due an USADE, use of the study device or Automated Mode will not be restarted until approval is received from the regulatory authorities.

Use of the investigational device by a participant will be discontinued if any of the following occur:

- The investigator, sponsor, or Medical Monitor believes it is unsafe for the participant to continue in the study for any reason. This could be due to the development of a new medical condition or worsening of an existing condition; or participant behavior contrary to the indications for use of the device that imposes on the participant's safety.
- The participant requests that the treatment be stopped
- Participant pregnancy
- Two distinct episodes of DKA as defined above
- Two distinct severe hypoglycemia events as defined above
- One episode of DKA and one severe hypoglycemia event as defined above

An additional requirement for continued study device use following a single DKA or severe hypoglycemia event will be that (1) the site investigator believes that the event is explainable, unlikely to recur, and that it is safe for the participant to continue to use the system and (2) the Medical Monitor concurs. If the Medical Monitor determines that the occurrence of the event indicates that it is not safe for the participant to continue to use the system, use will be discontinued, and the participant will be withdrawn from the study.

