7.9 Early Withdrawal

Any participant may withdraw from the study at any time for any reason. Upon withdrawal, assessments will be performed following Table 1: Schedule of Assessments and Table 2: Patient Reported Outcomes (Questionnaires). The investigator may also terminate a participant's participation in the study if it is in the best interest of the participant or if the Sponsor or local regulatory agency terminates the study.

The Early Withdrawal visit will include:

- A1C (central laboratory)
- Review of concomitant medications
- Weight
- Vital signs
- Assessment of AEs
- Insulin delivery metrics (e.g., TDI, average basal and bolus insulin dose, and time on device) (Control group only)
- Completion of questionnaires (Table 2: Patient Reported Outcomes (Questionnaires))
- Return BG meter, Ketone meter, and study CGM, if unused
- Return Omnipod 5 System (Intervention group only)
- Stop CGM data collection
- Data Portal discontinuation (Intervention group only)
- Complaints/device deficiencies such as occlusion alarms and system hazard alarms since last visit
- BG/ketone meter data review by clinician
- Pump and CGM data review by clinician

The reason for withdrawal will be recorded, and their participation in the study will end.

In the event of a participant's death during the study, the participant's participation will be considered terminated, and the date of death will be used as the date of study exit.

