9.4 Reportable Adverse Events

Adverse events will be assessed on an ongoing basis throughout the study. Adverse event reporting will begin at the start time of the standard therapy (i.e., insertion of the CGM sensor) and continue until the participant's participation has ended. All adverse events must be followed until resolution, or until the AE has stabilized, or until the study has been completed.

Pre-existing medical conditions or symptoms observed prior to the start time of the standard therapy phase will not be recorded as an AE and should be collected in the participant's medical history. In the event there is a change (i.e., worsening) in the pre-existing medical condition or symptoms after enrollment meeting the criteria of a reportable adverse event, then an AE must be reported.

For this protocol, a reportable adverse event includes any untoward medical occurrence that meets one of the following criteria:

1. An SAE
2. An ADE unless excluded from reporting in Hypoglycemic Events and Hyperglycemic/Ketotic Events sections below
3. An AE not related to a study device issue which leads to temporary or permanent discontinuation of the study devices or the participant's own insulin pump, or creates a clinically significant impact on a participant's glucose control
4. An AE that affects the participant's ability to complete any study procedures
5. An AE for which a visit is made to a hospital emergency department
6. Hypoglycemic Events as defined below
7. Hyperglycemia/Ketotic Events as defined

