9.9 Outcome of Adverse Events

The outcome of each reportable adverse event will be classified by the investigator as follows:

- Recovered/Resolved – The participant recovered from the AE/SAE without sequelae. Record the AE/SAE stop date.
- Recovered/Resolved with Sequelae – The event persisted and had stabilized without further anticipated change in the event status. Record the AE/SAE stop date.
- Fatal – A fatal outcome is defined as the SAE that resulted in death. Only the event that was the cause of death should be reported as fatal. AEs/SAEs that were ongoing at the time of death; however, were not the cause of death, will be recorded as “resolved” at the time of death.
- Not Recovered/Not Resolved (Ongoing) – An ongoing AE/SAE is defined as the event was ongoing with an undetermined outcome.
 - An ongoing outcome will require follow-up by the site in order to determine the final outcome of the AE/SAE or until participant completes the study.
 - The outcome of an ongoing event at the time of death that was not the cause of death, will be updated and recorded as “resolved” with the date of death recorded as the stop date.

- Unknown – An unknown outcome is defined as an inability to access the participant or the participant's records to determine the outcome (for example, a participant that was lost to follow-up).

If any USADEs are ongoing when a participant completes the study (or withdraws), the participant will continue to be followed until the event resolves or has no prospect of improvement or change, even after the participant has completed all applicable study visits/contacts, unless that participant has withdrawn their consent. For all other reportable adverse events, data collection will end at the time the participant completes the study. Note: Participants should continue to receive appropriate medical care for an adverse event after their participation in the study ends.

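### CGM time after a permanent Omnipod 5 stop is dropped in the Intervention arm only (SAP 7.1.1), and Protocol 10.1 does not secure follow-up after the device is stopped

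*Protocol*

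**What the plan says.** **CGM window (SAP 7.1.1).** For Intervention, the window ends at the last non-error reading taken with Omnipod 5, either up to Controller return or on the exit-visit date, whichever is earlier. For Control, it ends at the last CGM reading on the exit-visit date, with no condition on the pump. SAP 7.4 excludes readings after the window closes. SAP 7.6.1 averages all available readings into one value per participant once there are at least 2,016 (seven days). The primary analysis set is everyone randomized (SAP 7.2.2).

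**Stopping rules (Protocol 10.1).** After a single DKA or severe hypoglycemia event that the Medical Monitor judges to make system use unsafe, "use will be discontinued, and the participant will be withdrawn from the study". The other triggers come under a sentence about the device only: "Use of the investigational device by a participant will be discontinued if any of the following occur". One of those triggers is itself about participation, namely that the investigator, sponsor or Medical Monitor "believes it is unsafe for the participant to continue in the study for any reason". The section heading also speaks of study participation. After a USADE, the Medical Monitor may ask participants to stop the device, with no restart until regulators approve.

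**What withdrawal means.** Protocol 7.9 states: "The reason for withdrawal will be recorded, and their participation in the study will end". It also gives a discretionary exit that is not tied to an arm: "The investigator may also terminate a participant's participation in the study if it is in the best interest of the participant". Under Protocol 9.4, adverse event reporting will "continue until the participant's participation has ended".

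**The concern.** SAP 3.1 defines the primary endpoint as TIR on the study CGM over the 13-week randomized period. It does not restrict this to time on the device. The window rule adds that restriction for one arm, so the comparison is on-device for Intervention and on-study for Control.

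Permanent stops are likely to be linked to outcome: DKA, severe hypoglycemia, a device problem or dissatisfaction. If TIR falls when automated delivery ends, dropping the later time flatters the Intervention mean. The same window feeds time below 54, time above 180, mean glucose and time below 70.

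The planned sensitivity analyses do not test this. A shortened record with 2,016 readings is not missing, so direct likelihood, multiple imputation (SAP 4.3.2) and the tipping-point analysis (SAP 4.3.3) leave it as it is.

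The withdrawal rule matters for a related reason. Someone withdrawn under 10.1 has no later study CGM data and no new adverse events recorded. If the Early Withdrawal A1C or questionnaire falls outside the analysis window, the 13-week value is imputed under SAP 7.6.1.1.

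**Working it through.** **1. The plan's own figure.** Inputs from Protocol 11.5 and SAP 4.1: difference 10, SD 16.5, two-sided 5%, power 90%, ratio 2:1.

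- Normal approximation: Control n = 1.5 × (1.960 + 1.282)² × 16.5² / 10² = 42.9, so 43, and 129 in total.
- Noncentral t: 86/43 gives power 0.896 and 87/44 gives 0.902. The stated 131 reproduces.
- 131 / (1 − 0.229) = 170 and 170 / (1 − 0.15) = 200 also reproduce.
- SE of the difference with 87/44: 16.5 × √(1/87 + 1/44) = 3.05 points.

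**2. Who is affected.**

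| Situation | Intervention | Control |
|---|---|---|
| Stops the pump for good, stays on study | Window closes at last Omnipod 5 reading | Window runs to exit visit |
| Leaves the study early | Closes at or before exit | Closes at exit |
| Temporary gap | Not closed by the gap | Not closed by the gap |
| Manual Mode on Omnipod 5 | Not closed | Not applicable |

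The asymmetry lies in the first row.

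**3. Loss of TIR on stopping.** The documents give no direct estimate for this trial. Protocol section 1 (post-hoc crossover, n = 83) gives TIR of 62.7% on standard therapy, 74.4% in the first automated phase, 65.5% in manual mode and 73.6% in the second automated phase.

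- 73.6 − 65.5 = 8.1
- 74.4 − 65.5 = 8.9 (the actual on-to-off change)
- 74.4 − 62.7 = 11.7 (automated use against standard therapy)

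The range 8.1 to 11.7 is used as an assumption.

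**4. Overstatement per participant.** For a stop on day d of 91, overstatement = (91 − d)/91 × loss. Dividing by 113 (two thirds of 170) gives the shift in the Intervention mean.

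| Stop | Participant's value | Intervention mean |
|---|---|---|
| Halfway (day 45.5) | 0.5 × 8.1 to 0.5 × 11.7 = 4.05 to 5.85 | 0.036 to 0.052 |
| Day 7, with just 2,016 readings | 0.923 × 8.1 to 0.923 × 11.7 = 7.5 to 10.8 | 0.066 to 0.096 |

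**5. How many would matter.** Moving the Intervention mean by 1 point takes 113/5.85 = 19.3 to 113/4.05 = 27.9 halfway stoppers who remain on study.

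**6. Stress case.** Suppose a share equal to the whole 22.9% attrition allowance stopped halfway, stayed on study and lost the full 10-point effect. The effect with all CGM time kept would be 10 × (1 − 0.229 × 0.5) = 8.86. Power with 113/57 would be 0.907, against 0.960 at 10 points.

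**The case against.** **The affected group may be nearly empty.** The protocol describes no off-device follow-up, 10.1 is headed as a rule on participation, and the Early Withdrawal visit stops CGM collection. For ordinary withdrawals, both arms' windows end by exit. This largely stands and is why the effect is small. The group is not excluded, though: a USADE stop and most listed triggers end device use without ending participation.

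**Using Omnipod 5 may only name the data source.** SAP 7.4 takes endpoints from either a CGM or Omnipod 5, and Protocol 7.4 confirms Dexcom data transmission only for Control. This is a plausible account of why the rule was written. It does not change its effect, and Protocol 13.2.2 says CGM data are collected from the CGM device for all participants.

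**The seven-day rule treats both arms alike.** Correct. The rule is not a one-sided bias. The one-sided element is the end of the window.

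**Withdrawal after a confirmed safety failure is defensible, and safeguards exist.** Protocol 9.4 says "All adverse events must be followed until resolution, or until the AE has stabilized". For a USADE still ongoing at withdrawal, Protocol 9.9 says "the participant will continue to be followed until the event resolves". The triggering event and the Early Withdrawal assessments are kept. These provisions follow known events; they do not capture new events or CGM data after exit.

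**Stronger readings that the documents do not support.** A reader might infer that the single-event rule is written for Intervention alone. That is the natural reading, because it speaks of the study device and the system and follows the investigational-device criteria, but no arm is named and the Study Devices row of the Protocol Summary also lists the Control pump. A reader might also infer a measurable distortion of the severe hypoglycemia and DKA rates. The documents give no expected event rate and no share of events that would be judged unsafe, and these endpoints are exploratory, so no size can be put on it.

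**Conclusion.** The window asymmetry is real in the current SAP text, and no planned sensitivity analysis examines it. It favors Intervention if TIR falls on stopping. The size is about 4 to 6 TIR points for a participant who stops halfway, or 0.04 to 0.05 points on the Intervention mean for each such participant. This rests on the 8.1 to 11.7 point loss carrying over from a post-hoc comparison in an earlier single-arm trial.

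The number of participants who stop for good and stay on study is not given and cannot be derived. It would be tempting to conclude that the primary result is at risk, but it is not: a 1-point shift needs roughly 19 to 28 halfway stoppers, against a 10-point design effect and an SE of 3.05. What changes is mainly what is being estimated. The withdrawal rule in 10.1 is a related, secondary point, since it and the unclear wording for other triggers decide whether later CGM data exist at all. This is an improvement worth making, not a flaw that undermines the trial.

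**What to change.** **1. SAP 7.1.1.** End the Intervention window at the last non-error study CGM reading on the date of the study exit visit, regardless of the pump in use. Take readings after the last Omnipod 5 reading from the Dexcom G6 data feed. Keep the per-protocol set as the supportive on-device analysis.

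**2. Protocol 10.1.** Keep every device-stop trigger. End the single-event sentence once it has said that use is discontinued, and add a separate paragraph covering all triggers:

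> Participants who stop the study device return to usual insulin therapy and remain in follow-up on the study CGM, with adverse event collection and scheduled visits to Visit 8, unless they withdraw consent or continued study participation itself is judged unsafe or not in their best interest.

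The SAP edit alone recovers nothing for a participant withdrawn under 10.1, so the second edit is needed for the first to reach people stopped for safety. Collection off Omnipod 5 is already feasible: participants agree to use the Dexcom app throughout (inclusion criterion 6), and EU sites dispense a CGM data collection device (Protocol 7.2).

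**Cost.** A protocol amendment with the signatures, IRB/EC approval and regulatory filing in Protocol 14.6; a consent update; CGM supplies for a few participants at visits already scheduled; and possibly a slightly smaller estimated benefit.

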10.2 Criteria for Suspending or Stopping Overall Study

Error! Reference source not found. For unanticipated adverse device effects (USADEs), the Study Physician, together with the Medical Monitor per the Safety Management Plan (SMP), will determine whether the study should proceed or not based upon risk of additional serious adverse events and the underlying root cause analysis of the USADE.

Study activities could be similarly suspended if the manufacturer of any component of the investigational study device requires stoppage of device use for safety reasons (e.g., product recall).

The affected study activities may resume if the underlying problem can be corrected by a protocol or system modification that will not invalidate the results obtained prior to suspension.

The Study Physician and Medical Monitor may recommend suspension of study activities or stoppage of the study if deemed necessary based on the totality of safety data available.

10.3 Safety Signal Detection

Selected data from this study will be reviewed periodically to detect as early as possible any safety concern(s) related to the device so that Investigators, clinical study participants, regulatory authorities, and IRBs/IECs will be informed appropriately and as early as possible.

The Medical Monitor will conduct adjudication of any events of DKA or severe hypoglycemia or any additional events as requested by the Sponsor. The specified events will be adjudicated to determine:

- event relatedness to the study procedures and/or the devices (participant's own insulin pump, study CGM and Omnipod 5)
- whether an adverse event is unanticipated

The adjudication decision of the Medical Monitor will be used for the final classification of events, including relatedness to the study procedures and/or the devices, for the determination of safety endpoints and for all regulatory reports, product labeling, and publications or presentations.

Detailed roles and responsibilities of the Study Physician and Medical Monitor are described in the SMP.

11 STATISTICAL CONSIDERATIONS

11.1 Primary Endpoint and Hypotheses

The primary endpoint is per-participant percentage of time in range (TIR) 70-180 mg/dL as measured by study CGM and comparing the Intervention group to the Control group during the 13-week randomized period. The null hypothesis is that the mean percentage of TIR 70-180 mg/dL in the Intervention group is equal to the mean percentage of TIR 70-180 mg/dL in the Control group during the 13 weeks. The alternative hypothesis is that the mean percentage of TIR 70-180 mg/dL in the Intervention group is not equal to the mean percentage of TIR 70-180 mg/dL in the Control group during the 13 weeks.

Formally, the null and alternative hypotheses for the primary efficacy endpoint are:

$$H_0: \mu_I - \mu_C = 0$$

$$H_A: \mu_I - \mu_C \neq 0$$

Where μ_I and μ_C are the population means of per-participant percentage of TIR 70-180 mg/dL as measured by the study CGM during the 13 weeks in the Intervention and Control groups, respectively.

The primary endpoint will be analyzed with a linear mixed effects model with TIR 70-180 mg/dL during the 13-weeks as the outcome. The full model specification will be described in the SAP.

11.2 Secondary Endpoints and Hypotheses

The following secondary per-participant endpoints will be evaluated and compared in the Intervention group vs. Control group at the end of the 13-week randomized period:

- Percentage of time <54 mg/dL (non-inferiority)
- Percentage of time >180 mg/dL
- Mean glucose
- Change from baseline in A1C
- Percentage of time < 70 mg/dL
- Change from baseline in Type 1-Diabetes Distress Scale (T1-DDS) total score at 13 weeks
- Change from baseline in Hypoglycemia Confidence Scale (HCS) total score at 13 weeks
- Change from baseline in Diabetes Quality of Life-brief (DQOL-brief) total score at 13 weeks

Secondary Endpoints will be tested in a hierarchical fashion.

The null and alternative hypotheses for the secondary endpoints are as follows:

Percentage of time < 54 mg/dL (non-inferiority):

$$H_0: \mu_I - \mu_C \geq 1\%$$

$$H_A: \mu_I - \mu_C < 1\%$$

Where μ_I and μ_C are the population means of percentage of time < 54 mg/dL during the 13 weeks in the Intervention and Control groups, respectively. The non-inferiority margin is 1%. If the upper bound of the two-sided 95% confidence interval for the difference (μ_I

minus μ_c) is $<1\%$, non-inferiority will be established. If the upper bound of the two-sided 95% confidence interval for the difference (μ_i minus μ_c) is $<0\%$, superiority of the Intervention group compared to the Control group will be established.

Percentage of time >180 mg/dL:

$$H_0: \mu_i - \mu_c = 0$$

$$H_A: \mu_i - \mu_c \neq 0$$

Where μ_i and μ_c are the population means of percentage of time >180 mg/dL during the 13 weeks in the Intervention and Control groups, respectively.

Mean glucose:

$$H_0: \mu_i - \mu_c = 0$$

$$H_A: \mu_i - \mu_c \neq 0$$

Where μ_i and μ_c are the population means of mean glucose during the 13 weeks in the Intervention and Control groups, respectively.

Change from baseline in A1C:

$$H_0: \mu_i - \mu_c = 0$$

$$H_A: \mu_i - \mu_c \neq 0$$

Where μ_i and μ_c are the population means of change from baseline in A1C after 13 weeks in the Intervention and Control groups, respectively.

Percentage of time < 70 mg/dL:

$$H_0: \mu_i - \mu_c = 0$$

$$H_A: \mu_i - \mu_c \neq 0$$

Where μ_i and μ_c are the population means of percentage of time < 70 mg/dL during the 13 weeks in the Intervention and Control groups, respectively.

Change from baseline in Type 1-Diabetes Distress Scale (T1-DDS) total score at 13 weeks:

$$H_0: \mu_i - \mu_c = 0$$

$$H_A: \mu_i - \mu_c \neq 0$$

Where μ_I and μ_C are the population means of change from baseline in T1-DDS total score after 13 weeks in the Intervention and Control groups, respectively.

If change from baseline in T1-DDS total score after 13 weeks is found to be statistically significantly different in the Intervention group compared to the Control group, the proportion of subjects in each treatment group achieving an improvement of ≥ 2 points (MCID) in the T1-DDS total score after 13 weeks will also be compared. Those hypotheses are stated as:

$$H_0: \pi_I - \pi_C = 0$$

$$H_A: \pi_I - \pi_C \neq 0$$

Where π_I and π_C are the proportion of subjects achieving an improvement of 0.19 ≥ 2 points (MCID) in the T1-DDS total score after 13 weeks in the Intervention and Control groups, respectively.

Change from baseline in Hypoglycemia Confidence Scale (HCS) total score at 13 weeks:

$$H_0: \mu_I - \mu_C = 0$$

$$H_A: \mu_I - \mu_C \neq 0$$

Where μ_I and μ_C are the population means of change from baseline in HCS total score after 13 weeks in the Intervention and Control groups, respectively.

If change from baseline in HCS total score after 13 weeks is found to be statistically significantly different in the Intervention group compared to the Control group, the proportion of subjects in each treatment group achieving a score of ≥ 3 points in the HCS total score after 13 weeks will also be compared. Those hypotheses are stated as:

$$H_0: \pi_I - \pi_C = 0$$

$$H_A: \pi_I - \pi_C \neq 0$$

Where π_I and π_C are the proportion of subjects achieving a score of ≥ 3 points in the HCS total score after 13 weeks in the Intervention and Control groups, respectively.

Change from baseline in Diabetes Quality of Life-brief (DQOL-brief) total score at 13 weeks:

$$H_0: \mu_I - \mu_C = 0$$

$$H_A: \mu_I - \mu_C \neq 0$$

Where μ_I and μ_C are the population means of change from baseline in DQOL-brief total score after 13 weeks in the Intervention and Control groups, respectively.

If change from baseline in DQOL-brief total score after 13 weeks is found to be statistically significantly different in the Intervention group compared to the Control group, the proportion of subjects in each treatment group achieving a clinically meaningful improvement in the DQOL-brief total score after 13 weeks will also be compared. Those hypotheses are stated as:

$$H_0: \pi_i - \pi_c = 0$$

$$H_A: \pi_i - \pi_c \neq 0$$

Where π_i and π_c are the proportion of subjects achieving a clinically meaningful improvement (defined as ≥ 0.5 *standard deviation of change from baseline in DQOL-brief total score at 13 weeks) in the DQOL-brief total score after 13 weeks in the Intervention and Control groups, respectively.

Secondary endpoints will be analyzed using linear mixed effect models. The full model specifications will be described in the SAP.

